#### 4.0 SUMMARY OF PROTOCOL CHANGES

Summary of Changes to the Protocol			
Amendment Number	New Protocol Version and	Description of Change	Reason for Change
Number	Date		
NA	NA	NA	NA

# 5.0 PROTOCOL SYNOPSIS

Study Summary		
Julian Julian J		

Protocol Title	Clinical Evaluation of a Mobile App-Based Respiratory Device in the Emergency Department Setting
Short Name	CLEAR-ED
Study Objectives	The primary objectives of this study are to evaluate the agreement and usability of the new device, namely the purpleDx smartphone video technology, for measuring patients' peak expiratory flow, forced expiratory volume in one second, respiratory rate and heart rate when compared to results measured using standard clinical reference methods during a single patient encounter in an Emergency Department setting.
	The secondary objectives are to demonstrate the safety of the purpleDx smartphone application and determine any subject subgroups or conditions of use of the new device that impair the quality or reliability of data.
Study Procedures	Subjects will undergo measurement of peak expiratory flow, forced expiratory volume in one second, respiratory rate and heart rate at one ED visit, using standard medical equipment/means and using the smartphone application purpleDx. Results will be recorded and analysed to determine the agreement and variation between traditional and new medical devices in this setting.
Study Sponsor	electronRx Ltd
Sponsor Representative	[name]
Study Design	This is a prospective, comparative, single-visit medical device study to collect data to support a marketing application in the UK and EU. There is no Investigational Medicinal Product in this study. All subjects will undergo testing with traditional medical equipment/means and the Investigational Medical Device, purpleDx, thus each subject

	will act as their own control.	
Investigational Medical Device	purpleDx is a non-interventional smartphone application which measures peak expiratory flow, forced expiratory volume in one second, respiratory rate and heart rate utilising the camera function and enhanced video quality of such mobile phones. It is categorised as Class IIA Software as a Medical Device (SaMD) and has been developed by electronRx Ltd in Cambridge.	
Study Location	Cambridge University Hospitals NHS Foundation Trust (CUH)	
	Emergency Department	
	Addenbrooke's Hospital	
	[name]	
	Cambridge	
	[name]	
Study Duration	Two months from date of site initiation visit to date of last subject recruited into the study.	
Subject Population	Subjects will be male or female, aged 18 years and above, and must be able to sit up and read, understand and write in English. Subjects with and without a diagnosis of respiratory or cardiopulmonary disorder/s will be included.	
Sample Size	Maximum of 160 subjects.	
Primary Endpoint	Demonstration that measurements for physiological signals of peak expiratory flow obtained using purpleDx sufficiently agree with those obtained using standard clinical equipment/means to proceed to marketing application.	
Secondary Endpoints	Demonstration that measurements for physiological signals of forced expiratory volume in one second, respiratory rate and heart rate obtained using purpleDx sufficiently agree with those obtained using standard clinical equipment/means to support	

	proceeding to marketing application.
	
 
Establishment of thresholds for 'normal' ranges for peak expiratory flow, forced expiratory volume in one second, respiratory rate and heart rate.
 

	

Demonstration of usability and ease of use of purpleDx by subjects and clinical staff.

	4) Demonstration of the safety of purpleDx.
	

Determination of any subsets of the patient population for which purpleDx may not be suitable.

	
 
Determination of any conditions or situations which impair the recording quality or reliability of data produced by purpleDx.
 

Reference Standards	
 
Medical UK Devices Regulation 2002 (SI 2002 No 618, as amended) [Part II is the relevant section for general medical devices including SaMD]
 

	
 
Medical Device Regulation (EU) 2017/745
 

	
 
ISO 13485:2016 Medical devices – Quality management system – Requirements for regulatory purposes
 

	
 
ISO 14155:2020 Clinical Investigation of Medical Devices for Human Subjects – Good Clinical Practice
 

	
 
ISO 14155-1:2009 Clinical Investigation of Medical Devices for Human Subjects – General Requirements
 

	
 
ISO 14155-2:2009 Clinical Investigation of Medical Devices for Human Subjects – Clinical Investigation Plan
 

	
 
IEC 62366-1 Part 1: Application of usability engineering to medical devices
 

	
 
IEC 62304:2006 Medical device software – Software life cycle processes
 

	
 
IEC 82304-1:2016 Health software Part 1: General requirements for product safety
 

	
 
Declaration of Helsinki 2024 – Medical Research
 

	Involving Human Participants	
	
 
ICH GCP E6(R2): Guideline for Good Clinical Practice 2016
 
	
Health Economics	Utilisation of smartphones to enable patients to monitor and submit data to medical consultants for appraisal could revolutionise the identification and management of long-term health conditions such as asthma, Chronic Obstructive Pulmonary Disease and Interstitial Lung Disease. If a clinician could access the information held in the application, they may be able to amend a patient's treatment regime as clinically indicated following review of real-time data that	
	could be compared to historical results, potentially without the need for the patient to attend a hospital clinic. This would alleviate demand for clinic slots, whilst simultaneously reducing waiting time and travel burden for patients, helping to revolutionise the patient management pathway.	
Randomisation	Not applicable as there are no treatment arms in this study. Each subject will act their own control, by being tested with standard medical equipment and with purpleDx.	
Eligibility Criteria	Inclusion Criteria	
	Sex at birth classified as male or female	
	2) 18 years of age and above, presenting to CUH     Emergency Department	
	Able to read and understand the patient information sheet in English	
	4) Capacity and ability to sign an informed consent form	
	5) With or without respiratory or cardiorespiratory symptom/s	
	Exclusion Criteria	
	1) Unable to sit up i.e. cannot lie completely flat (supine)	
	2) Known pregnancy in women of child-bearing potential	
	Unable to comply with the requirements of the investigation in any way	

4) Prisoners or young offenders	
---------------------------------	--

#### 6.0 **ACRONYMS AND DEFINITIONS**

Acronym	Definition
ADE	Adverse Device Effect
AE	Adverse Event
AF	Atrial Fibrillation
арр	Smartphone Application
bpm	beats per minute
CA	Conformity Assessment
CI	Chief Investigator
COPD	Chronic Obstructive Pulmonary Disease
CTCAE	Common Terminology Criteria for Adverse Events v5.0
CUH	Cambridge University Hospitals NHS Foundation Trust
DD	Device Deficiency
DPO	Data Protection Officer
ECDS	Emergency Care Data Set
eCRF	Electronic Case Report Form
ED	Emergency Department
EU	European Union
FEV 1	Forced Expiratory Volume in One Second
GB	Great Britain (England, Scotland and Wales)
GCP	Good Clinical Practice
GDPR	General Data Protection Regulation
HR	Heart Rate
HRA	Health Research Authority

ICC	Intraclass Correlation Coefficient
ICF	Informed Consent Form
ICH	International Conference on Harmonisation
ICO	Information Commissioner's Office
IEC	International Electrotechnical Commission
IFU	Instructions For Use
ILD	Interstitial Lung Disease
IMD	Investigational Medical Device
IRAS	Integrated Research Application System
ISF	Investigational Site File
ISO	International Organization for Standardization
LOA	Limits of Agreement
MDR 2002	Medical Devices Regulations 2002 (SI 2002 No 618, as amended)
MDR (EU)	Medical Device Regulation (EU) 2017/745
MHRA	Medicines and Healthcare products Regulatory Agency
NA	Not Applicable
NCRV	National Contract Value Review
NHS	National Health Service
NICE	National Institute for Health and Care Excellence
NIHR	National Institute for Health and Care Research
PAH	Pulmonary Arterial Hypertension
PEF	Peak Expiratory Flow
PID	Participant Identifiable Data
PIS	Patient Information Sheet
POC	Proof of Concept
purpleDx	Medical Device under Investigation in this Clinical Study
QMS	Quality Management System

REC	Research Ethics Committee
RN	Research Nurse
ROC	Receiver Operating Characteristics
RR	Respiratory Rate
SADE	Serious Adverse Device Effect
SAE	Serious Adverse Event
SaMD	Software as a Medical Device
SAP	Statistical Analysis Plan
SD	Standard Deviation
SDV	Source Data Verification
SIV	Site Initiation Visit
SOP	Standard Operating Procedure
SSA	Site-Specific Approval
TMF	Trial Master File
UK	United Kingdom
UKCA	UK Conformity Assessment
USADE	Unanticipated Serious Adverse Device Effect
WHO	World Health Organisation
WOCBP	Women of Child-Bearing Potential

#### 7.0 INTRODUCTION

## 7.1 Background

The ubiquitous distribution of smartphones amongst all population socioeconomic groups worldwide makes smartphone exploitation to access healthcare data a new axiom to stimulate change in the healthcare system. Indeed, in 2024, the Global System for Mobile Communications (GSM Association) stated that smartphones were owned by 57% of the global population, a staggering 4.6 billion people and the numbers are growing. The prevalence of smartphones combined with consumer willingness to adopt novel technology provides an opportune platform to enable the healthcare sector to revolutionise and streamline the management of patients on a

platform that is already available to millions. Utilisation of smartphones can empower the public to use healthcare more efficiently and the technology has the potential to enable clinicians to make more rapid and accurate treatment decisions, reducing patient waiting times and freeing up clinic appointments to increase the number of patients that can be dealt with over a given time. This is of particular importance given the increasing demand on health services due to the complex healthcare needs of an ageing population.

The field of respiratory medicine lends itself to the introduction of smartphone technology to improve the care pathway for patients with long-term conditions such as Chronic Obstructive Pulmonary Disease (COPD), Interstitial Lung Disease (ILD), Pulmonary Arterial Hypertension (PAH) and/or asthma. Currently, patients' physiological data, such as peak expiratory flow, forced expiratory volume in one second, respiratory rate and heart rate, is only collected by healthcare professionals when the patient attends hospital clinic visits, with no data collection during the intervening periods. In addition, there may be lengthy delays to accessing spirometry in the current NHS setting outwith the conventional follow up clinic structures. Indeed, there is considerable support in the extensive literature devoted to exploring the added value of home-based respiratory monitoring in at-risk groups to control disease, alter medication use and reduce hospital admissions as in COPD and Asthma. However, patients could assume a much more active role in their monitoring by downloading an application (app) such as purpleDx, onto their smartphones to generate data which could then be collated and securely stored in a cloud-based database in accordance with the General Data Protection Regulation (GDPR) requirements, building a repository of comprehensive data indicative of the individual patient's clinical profile over real time. Subsequently, if a patient became concerned that their clinical condition was deteriorating, the intention could be for their clinician to be alerted to consider any changes in purpleDx data amassed over time in conjunction with discussion of changing symptomology (such as increased breathlessness, cough or fatigue). The clinician may then be able to remotely affect changes to the subject's medication regimen to alleviate the issues being experienced quickly and without the need for them to attend the clinic. This early detection of exacerbations and consequent prompt treatment modification or introduction would provide a novel approach, for streamlined and personalised management of patients with long-term respiratory conditions, potentially saving time and resources5.6.7,8 and offering healthcare cost benefits.

The idea of using smartphone apps to aid clinical decision-making is not new and a variety of apps already exist on the market, such as the iPhone iSeismometer app which measures tremor frequency instead of the need costly for electromyogram analysis. Other examples of similar technology beginning to impact on healthcare would be FitBit and Apple watches now used widely for monitoring of atrial fibrillation (AF). The National Institute for Health and Care Excellence (NICE) in the UK has also

drawn attention to these devices singling out the Kardia device as a readily portable adjunct to the smartphone for AF monitoring. The simplicity of use versus the accuracy continues to be subject to controversy but the foothold these devices now have in the public domain confirm the enormous importance they represent for improving and extending healthcare initiatives. In the UK, before a new app can be approved for recognised clinical use, an MHRA approved clinical study must be carried out to 'verify that under normal conditions of use the performance characteristics of the device are those intended by the manufacturer and determine any undesirable side effects under normal conditions of use and assess whether these constitute risks when weighed against the intended performance of the device'. Rigorous international standards must be complied with, including ISO13485:2016 and IEC 62366-1, and requirements are dependent on the level of risk posed by the medical device. This represents the major difference from 'Wellbeing' apps which are unproven and may over-diagnose or worse, under-diagnose critical issues of relevance to individual patients and their ongoing care.

This protocol aims to obtain clinical data to support the MHRA classification of this device and verify the broad equivalence of purpleDx and traditional medical equipment/means (Vitalograph spirometer, manual respiratory count and pulse oximeter), to measure four physiological parameters, namely peak expiratory flow (PEF), forced expiratory volume in one second (FEV1), respiratory rate (RR) and heart rate (HR) in subjects with or without respiratory or cardiopulmonary conditions. The clinical data will be analysed and used to support a marketing application. Thus, establishing the data produced by smartphone and traditional devices/means is comparable for the measurement of physiological parameters is of paramount importance.

## 7.2 The Investigational Medical Device

The medical device under investigation in this study is a smartphone application (app), called purpleDx which has been developed by electronRx Ltd. It will be used to assess peak expiratory flow (PEF), forced expiratory volume in one second (FEV1), respiratory rate (RR) and heart rate (HR) by a non-contact scan utilising the phone's camera function. According to the classification of Medical Devices by the Medicines and Healthcare products Regulatory Agency (MHRA) in the UK and the Medical Device Regulation in Europe (MDR EU), the app should be classified as Class IIA Software as a Medical Device (SaMD) and is currently pending approval for clinical use. Class IIA is medium risk as it has the potential to be used to inform changes to treatment regime if the app was further developed for such purposes.

The purpleDx app is designed to be easy to use, with two non-contact scans captured over the course of just one minute each. The subject should ideally sit on a chair in a

relaxed, upright position, preferably with their back against the chair. Alternatively, the subject may recline on a bed or trolley, with a note made of the corresponding angle of recline. The smartphone must be immobilised by using a phone stand or by being propped against a sturdy object. The phone should be perpendicular to the subject. The first one-minute scan is to determine Breath Scan namely Peak Expiratory Flow (PEF), Forced Expiratory Volume in One Second (FEV1), and Respiratory Rate (RR), employing reference markers affixed to the subject's hands (one on each hand) to aid with visual tracking. The second one-minute scan is a Pulse Scan to measure Heart Rate (HR).

For PEF, FEV1 and RR, the subject presses 'Breath Scan' on the smartphone and must then adjust their camera image profile on the screen according to the on-screen instructions. Once the image is correctly aligned, the recording starts automatically. A countdown of the sixty-second recording period will be displayed on the screen during the scan. The app will save the scan results to the cloud for analysis. The Breath Scan will be carried out 3 times. When the automatic analysis from the 3 Breath Scans is complete, the PEF, FEV1 and RR results will be displayed on a results screen.

For HR, the subject presses 'Pulse Scan' and follows the on-screen instructions to position their face to fit the oval shown on the screen. Once the face is correctly positioned, the app will automatically start the recording. A countdown of the sixty-second recording period will be displayed on the screen during the scan. The HR results will appear after each Pulse Scan has been performed.

Screenshots of the various app screens are shown in Appendix 2.

Although not done as part of this clinical protocol, data could potentially be collated over time as the patient performed sequential testing.

#### 7.3 Research Data to Date

The purpleDx app is the culmination of an extensive body of developmental work that has been carried out by electronRx over the past four years. Initial Proof of Concept (POC) testing, and subsequent in-house verification and validation testing, has been undertaken using previous iterations of several electronRx apps over the course of the developmental process, namely Blueprint and rCP. These earlier generations of the app were used in the primary care setting to capture video signal data from a number of subjects. The resultant data were analysed and used to adjust and inform the algorithms for the metrics to be captured in this clinical study, such that purpleDx has arisen from the learnings of the previous app investigations.

POC testing was undertaken on 98 subjects in a clinic setting in Japan to demonstrate the rCP app can perform a one-minute scan of the subject to produce results for heart

rate and respiratory rate. Approximately 400 additional subjects have undergone testing during the programme of verification and validation testing in the UK, mainly utilising the Blueprint and rCP apps but also a small number using purpleDx. The results of the user testing have been used to hone the algorithms for purpleDx to maximise the reliability of the parameter measurements for this clinical trial protocol.

Data accrued so far from approximately 500 subjects demonstrated improvement in agreement of measurements using the new device compared to the standard clinical devices (e.g. Vitalograph spirometer and pulse oximeter), as iterations in the algorithms used were improved. Following discussion with clinical experts in respiratory function, the thresholds for clinically useful agreement between the measurements from existing clinical devices and those achieved using the new smartphone device have been defined as targets for this clinical trial (see Table of Limits below).

In addition, we have also noted that as well as offering multiplication in accessibility to such clinical data the smartphone device offers considerable benefits to users in ease of capture of this data. We have also recognised for respiratory functions, that worsening clinical condition increases variation in an individual's sets of readings but on the other hand that often subjects find using the new device easier when they are clinically worse. Thus, as well as looking at parameter agreement we have included an analysis of 'usability' which we will link to clinical status.

#### 7.4 Table 1: Table of Limits

This table shows the clinically acceptable variation in measurement between the new device and standard devices to remain clinically useful.

Parameter	Performance Range	Likely Performance of Device  (% Within Limits of Reference Values)	Bias Target	Expected Acceptable Level Of Agreement
PEF	350 – 700 L/min	≥ 80% within ± 20%	± 10%	± 20%
FEV 1	2-5L	≥ 95% within ± 10%	± 0.1 L	± 0.2 – 0.25 L

RR	6 – 20 breaths per minute (Bpm)	≥ 95% within ± 10%	± 2 Bpm	± 4 Bpm
HR	50 – 120 beats per minute (bpm)	≥ 95% within ± 10%	± 5 bpm	± 1 bpm

This table details the current range for which data has been obtained. It states the expected capacity of the new device to determine the reference value based on the population data currently available (i.e. the agreement between devices). The table also proffers an estimate of the bias expected and the potential performance of the new device at determining reference values in practice across an unknown population as expected in this study.

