## 14.9 Example Estimated Results Table

Parameter	Performance Range	Likely Performance of Device  (% Within Limits of Reference Values)	Bias Target	Expected Acceptable Level Of Agreement
PEF	350 – 700 L/min	≥ 80% within ± 20%	± 10%	± 20%
FEV 1	2-5L	≥ 95% within ± 10%	± 0.1L	± 0.2 – 0.25 L
RR	6 – 20 breaths per minute (Bpm)	≥ 95% within ± 10%	± 2 Bpm	± 4 Bpm
HR	50 – 120 beats per minute (bpm)	≥ 95% within ± 10%	± 5 bpm	± 2 bpm

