# 14.10 Estimand Table

Component	PEF	FEV 1	RR	HR
Treatment	Measurement using new device	Measurement using new device	Measurement using new device	Measurement using new device
Comparator	Vitalograph spirometer	Vitalograph spirometer	Manual count	Pulse oximeter
Population	Adults ≥18 years presenting to ED with respiratory / cardiorespiratory symptoms	Same as PEF	Same as PEF	Same as PEF
Variable (Endpoint)	Peak Expiratory Flow; PEF (L/min)	Forced Expiratory Volume in One Second; FEV 1 (L)	Respiratory Rate; RR (Breaths per minute)	Heart Rate; HR (beats per minute)
Summary Measure	Mean bias, 95% Limits of Agreement, % within ± 20% of reference	Mean bias, 95% Limits of Agreement, % within ±10%	Mean bias, 95% Limits of Agreement, % within ±10%	Mean bias, 95% Limits of Agreement, % within ±10%
Handling of Missing Data	Exclude invalid readings; perform sensitivity analysis if needed	Same as PEF	Same as PEF	Same as PEF
Intercurrent Events	Poor technique, device malfunction	Spirometry effort failure, device errors	Talking during measurement, movement artefact	Movement artefact, device connectivity issues
Interpretation	Agreement sufficient for clinical decision support at bedside	Agreement comparable to spirometry for diagnosis and monitoring	Agreement sufficient for respiratory distress assessment and monitoring	Agreement sufficient for accurate triage and monitoring

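### The heart rate acceptable-agreement limit is ±1 bpm in two tables and ±2 bpm in a third, and both are narrower than the ±5 bpm bias target beside them

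*Protocol*

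**What the plan says.** The same four-parameter table appears three times in the Protocol: in 7.4, in 14.3.5 and in 14.9. Each row ends with three entries: the percentage of readings expected within a band, the bias target, and the acceptable level of agreement.

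- **7.4 and 14.3.5, HR:** "≥ 95% within ± 10% ± 5 bpm ± 1 bpm"
- **14.9, HR:** "≥ 95% within ± 10% ± 5 bpm ± 2 bpm"

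The stated HR performance range is 50 to 120 bpm in all three.

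On the status of these figures, section 7.3 says that the agreement thresholds "have been defined as targets for this clinical trial (see Table of Limits below". Section 7.4 opens with "This table shows the clinically acceptable variation in measurement between the new device and standard devices to remain clinically useful". The heading of 14.3.5 calls its entries acceptable agreement thresholds. The estimand table in 14.10 lists the HR summary measures as "Mean bias, 95% Limits of Agreement, % within ±10" per cent.

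The formal success rule lies elsewhere. Sections 14.3.2 and 14.4.3 judge HR on the proportion of subjects whose paired readings agree within a percentage band, and the result is positive if the Wilson lower confidence bound is at least 80%.

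**The concern.** There are two separate inconsistencies. The first is between tables: ±1 bpm against ±2 bpm, with the rest of the row unchanged and nothing in the text to explain it. The second is within the row: the limit for agreement is tighter than the target for mean bias. Limits of agreement are the bias plus and minus a spread, so a limit on them would normally be wider than a limit on the bias alone. The PEF, FEV₁ and RR rows follow that order; only HR reverses it.

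HR agreement is a secondary endpoint meant to support a marketing application. Section 14.3.1 plans bias and limits of agreement as the standard agreement analysis, and this column holds the only bpm figure with which the HR limits of agreement could be compared. If the figure is uncertain, whether the HR Bland-Altman result is acceptable depends on which table or column the reader consults, and that choice could be made after the data are known.

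**Working it through.** **1. The plan's own figures for HR.** Section 14.4.3 takes the HR sample size from the FEV₁ calculation in 14.4.2, with n = 150, p₁ = 0.95 and two-sided α = 0.05:

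power = Φ{[(p₁ − p₀)√n − 1.96√(p₀(1 − p₀))] / √(p₁(1 − p₁))}

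For p₀ = 0.88: (0.07 × 12.247 − 1.96 × 0.325) / 0.218 = 1.01, so power is 84.4%. The four stated powers (99%, 84%, 71%, 54%) are reproduced as 99.2%, 84.4%, 71.2% and 54.5%. No bpm limit enters this formula, so the inconsistency does not touch the sample size.

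**2. Agreement limit divided by bias target, row by row (7.4, 14.3.5, 14.9).**

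| Parameter | Bias target | Agreement limit | Ratio |
|---|---|---|---|
| PEF | ±10% | ±20% | 2 |
| FEV₁ | ±0.1 L | ±0.2 to 0.25 L | 2 to 2.5 |
| RR | ±2 | ±4 | 2 |
| HR (7.4, 14.3.5) | ±5 bpm | ±1 bpm | 0.2 |
| HR (14.9) | ±5 bpm | ±2 bpm | 0.4 |

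**3. The ±10% band in bpm.** 0.10 × 50 = 5, 0.10 × 80 = 8 and 0.10 × 120 = 12, so the band is ±5 to ±12 bpm. Conversely, ±1 bpm is 2.0% of a reading of 50 and 0.83% of a reading of 120; ±2 bpm is 4.0% and 1.67%.

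**4. What the narrow limit implies.** The limits of agreement are bias ± 1.96 SD. For them to lie inside ±L, |bias| + 1.96 SD must not exceed L. With L = 1, |bias| cannot exceed 1 bpm and SD cannot exceed 1/1.96 = 0.51 bpm. With L = 2, the bounds are 2 bpm and 2/1.96 = 1.02 bpm. The ±5 bpm bias target can then never be the binding criterion.

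**5. Illustrations.** The Protocol gives no SD for HR differences, so normal differences and the values below are assumptions. The share within ±L is Φ((L − bias)/SD) − Φ((−L − bias)/SD).

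- *HR 80, bias 3, SD 1.* Within ±8 bpm (±10%): Φ(5) − Φ(−11), over 99.9%. Limits of agreement: 3 ± 1.96, or +1.04 to +4.96 bpm. Within ±1: Φ(−2) − Φ(−4) = 2%. Within ±2: Φ(−1) − Φ(−5) = 16%. The device meets the bias and percentage targets but misses either agreement limit.
- *Zero bias, exactly 95% within ±10%.* SD = 0.10 × HR / 1.96:

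| HR | SD (bpm) | Limits of agreement (bpm) | Within ±1 | Within ±2 |
|---|---|---|---|---|
| 50 | 2.55 | ±5 | 31% | 57% |
| 80 | 4.08 | ±8 | 19% | 38% |
| 120 | 6.12 | ±12 | 13% | 26% |

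- *Bias 0, SD 0.4.* Limits of agreement are ±0.78 bpm. This device meets all three criteria.

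**The case against.** The strongest reply is that the HR decision does not use this column. The only stated HR success rule is the Wilson lower bound on a proportion within a percentage band, and it gives the same answer whether ±1 or ±2 bpm is printed. Section 14.3.1 plans limits of agreement but sets no pass mark for them. This stands. A reader might infer that the same HR data would give opposite formal verdicts depending on the table used; the documents do not support that.

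A reader might also infer that any device meeting the bias and percentage targets must fail the agreement limit. That goes too far as well. The last illustration meets all three, and a tight limit makes the bias target redundant rather than logically impossible. The correct statement is that such a device can fail.

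The status of the column can be disputed too. The text below the table in 7.4 speaks of expected capacity and estimated bias, the column is never defined as a bound on limits of agreement, and 14.9 is titled as an example. But 7.3 and the opening of 7.4 give the figures target or acceptability status, and 14.9 repeats the rest of the HR row unchanged. Even as estimates, ±1 and ±2 bpm differ without explanation.

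Finally, a mismatch with the percentage band is not peculiar to HR. For RR, ±10% of 6 to 20 is ±0.6 to ±2 breaths per minute, against an agreement limit of ±4. For FEV₁, ±10% of 2 to 5 L is ±0.2 to ±0.5 L, against ±0.2 to 0.25 L. This stands: what is peculiar to HR is the reversed order of bias target and agreement limit, and the differing values between tables.

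**Conclusion.** The HR row is wrong as written and should be fixed. Two values are given for one limit, and both are narrower than the bias target in the same row, at 0.2 or 0.4 times that target against 2 to 2.5 times for the other parameters. These facts, and the redundancy of the ±5 bpm bias target under either limit, need no distributional assumption. The illustrated shares rest on assumed normal differences and chosen values of bias and SD; they show what can happen, not what the device is expected to do.

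The consequence is confined to how the HR Bland-Altman result is judged. The Wilson rule for HR, the sample size and the primary PEF endpoint are not affected. It may be tempting to conclude that the agreement limit is the misprint and must be widened, but the documents do not show whether the bias target, the agreement limit or both are in error.

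**What to change.** Before any data are seen, reconcile the HR rows in 7.4, 14.3.5 and 14.9 so that one bias target and one agreement limit appear throughout, with the agreement limit not narrower than the bias target. The sponsor and its clinical experts should decide which figure is in error and what the value is. Add one sentence saying that the full limits of agreement (bias ± 1.96 SD) are compared with that limit, and one on how this comparison relates to the ±10% proportion criterion, in particular which of the two decides if they disagree.

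The cost is a wording change to one row in up to three tables and two added sentences. It needs no extra patients or data and no change to the sample size.
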